6.13. Subgroup Analyses

6.13.1. Efficacy Subgroup Analyses

Subgroup analysis will be conducted for the primary endpoints of proportion of patients achieving an ASAS40 response at Week 16 (NRI) using the ITT Population for Period 2. The major secondary efficacy endpoints, the proportion of patients achieving ASAS20 (NRI) at Week 16, will also be conducted.

For categorical response variables (ASAS20 and ASAS40), a logistic regression analysis with treatment, subgroup, and of treatment-by-subgroup interaction included as factors will be used. The treatment-by-subgroup interaction will be tested at the 10% significance level. Treatment group differences will be evaluated within each subgroup using the Fisher's exact test, regardless of whether the interaction is statistically significant. If any group within the subgroup (for example, yes, no) is <10% of the total population, only descriptive statistics will be provided for that subgroup (that is, no inferential testing).

Forest plots may be created to illustrate the treatment differences with 95% CIs between each of the ixekizumab treatment groups and placebo group, by each subgroup category.

The following subgroups will be analyzed:

- Patient Demographics Subgroups:
 - Sex
 - Age category: <40 years, ≥40 years
 - Age category: <50 years, ≥50 years
 - Age category: <65 years, ≥65 years
 - Weight: <70 kg, ≥70 kg
 - BMI: underweight (<18.5 kg/m²); normal (≥18.5 and <25 kg/m²); overweight (≥25 and <30 kg/m²); obese (≥30 and <40 kg/m²); or extreme obese (≥40 kg/m²)
 - Ethnicity: Hispanic/Latino, Non-Hispanic/Non-Latino
 - Race: American Indian/Alaska Native, Asian, Black/African American, Native Hawaiian or other Pacific Islander, White, or Multiple
- Geographic Region Subgroups:
 - Geographic region: US (including Puerto Rico sites) or ROW
 - Geographic region: Europe or Non Europe
 - Geographic region: North America (US including Puerto Rico, Canada), ROW
 - Geographic region: America, Asia, Europe, and ROW
- Baseline Severity of Disease Subgroups:
 - Baseline (CRP categories):
 - ≤3.00 mg/L or >3.00 mg/L
 - ≤5.00 mg/L or >5.00 mg/L
 - ≤10.00 mg/L or >10.00 mg/L

- ≤ 15.00 mg/L or > 15.00 mg/L
- Baseline MRI status:
 - ASSpiMRI-Berlin score > 0 or $= 0$
 - SPARCC Spine score ≥ 2 or < 2
- Number of prior TNFi used: 1 or 2
- Baseline BASDAI:
 - $4 \leq$ BASDAI < 6 or BASDAI ≥ 6
- Baseline ASDAS:
 - ASDAS ≤ 3.5 or ASDAS > 3.5
- Other Patient Characteristics Subgroups:
 - Duration of symptom since axSpA onset category: < 10 years or ≥ 10 years
 - Duration of symptom since axSpA onset category: < 5 years or ≥ 5 years
 - Duration of symptom since axSpA of onset category: < 3 years or ≥ 3 years
 - HLA-B27 status: positive or negative
 - Smoking status: current or former/never
 - Concomitant cDMARDs (methotrexate, sulfasalazine, hydroxychloroquine) at baseline: yes or no
 - History of arthritis: yes or no
 - History of uveitis: yes or no
 - History of dactylitis: yes or no
 - History of psoriasis: yes or no
 - History of enthesitis: yes or no
 - History of inflammatory bowel disease: yes or no
 - History of extra-axial involvement: yes or no

Additional subgroup analyses on efficacy may be performed as deemed appropriate and necessary.

6.13.2. Safety Subgroup Analyses

Safety subgroup analysis for common TEAEs and AESI of allergy reaction/hypersensitivity and infections will be summarized by treatment group and overall, using the safety population for Period 2. The common TEAEs will be presented by MedDRA PT within SOC. The AESI of allergy reaction/hypersensitivity will be presented by anaphylaxis and nonanaphylaxis events, by PT within category. The AESI of infection will be presented by PT.

A logistic regression model with treatment, subgroup, and the interaction of subgroup-by-treatment included as factors will be used. The subgroup-by-treatment interaction will be tested at the significance level of 0.10. The response variable will be each AE. Treatment groups' differences will be evaluated within each category of the subgroup using Fisher's exact test, regardless of whether the interaction is statistically significant. If any group within the subgroup is $< 10\%$ of the total population, only the descriptive statistics will be provided for that subgroup (that is, no inferential testing).

The subgroups include baseline demographics and geographic region, which are defined as in Section 6.13.1.

Additional subgroup analyses on safety may be performed as deemed appropriate and necessary.

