5.3. Determination of Sample Size

Approximately 300 patients will be randomized at a 1:1:1 ratio in the Blinded Treatment Dosing Period (Period 2) to ixekizumab 80 mg Q2W, ixekizumab 80 mg Q4W, and placebo. With 100 patients per treatment group, CCI

these assumptions are based on the review of historical clinical studies in rad-axSpA (etanercept, adalimumab, infliximab, certolizumab, and golimumab [Davis et al. 2003; van der Heijde et al. 2005, 2006; Inman et al. 2008; Landewé et al. 2014]) and recent secukinumab data in patients who are TNF inhibitor experienced (Baeten et al. 2014; Sieper et al. 2014).

6. A Priori Statistical Methods

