6.1.1. General Considerations for Analyses during the Blinded Treatment Dosing Period (Period 2)

Comparisons between each ixekizumab regimen (80 mg Q2W or 80 mg Q4W) and placebo will be performed for all analyses in Period 2.

Period 2 starts at the first injection of study treatment at Week 0 (Visit 2) and ends before the first injection of study treatment at Week 16 (Visit 8) or the early termination visit (ETV) (between Weeks 0 and 16).

Baseline will be defined as the last available value before the first injection for efficacy, health outcome, and safety analyses. In most cases, this will be the measure recorded at Week 0 (Visit 2). For efficacy measures, if the patient does not take any injection, the last available value on or before randomization date will be used. Change from baseline will be calculated as the visit value of interest minus the baseline value. For safety analyses using a baseline period, the baseline period is defined as the time from Visit 1 to the date/time of the first injection.

The randomization to treatment groups is stratified by country, screening CRP status (nonelevated versus elevated), and number of prior TNF inhibitors used (1 or 2) as described in Section 5.2. The countries will be categorized into geographic regions for analysis. Geographic regions are defined in Section 6.2. Unless otherwise specified, the statistical analysis models will adjust for geographic region, baseline CRP status, and number of prior TNF inhibitors used.

Unless otherwise specified, treatment groups of ixekizumab 80 mg Q2W and Q4W groups will be analyzed without regard to starting dose.

The primary analysis method for treatment comparisons of categorical efficacy and health outcomes variables at specific time points will be made using a logistic regression analysis with treatment, geographic region (Europe and non-Europe), number of prior TNF inhibitors used, and baseline CRP status in the model using PROC Logistic with a Wald test. The odds ratio and 95% CIs will be reported; treatment difference and 95% CI will also be reported. Secondary analysis will be conducted using a Fisher's exact test. In the case when the logistic regression model does not produce statistical results due to sparse data, Fisher's exact test will be used.

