6.12.2.1. Common Adverse Events

Common TEAEs are those TEAEs that occurred in $\geq 1\%$ before rounding of total ixekizumab-treated patients.

The following tables will be provided for common TEAEs by treatment group and study period. When SOC is presented, then events will be ordered by decreasing frequency in the total ixekizumab group, within SOC. When SOC is not presented, then events will be ordered by decreasing frequency in the total ixekizumab group.

The following summaries will be provided for common TEAEs based on the Safety Population for Period 2:

- Common TEAEs by PT nested within SOC
- Common TEAEs by PT
- Common TEAEs by maximum severity by PT nested within SOC

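### The safety subgroup interaction test has no minimum event count and no named statistic; if Wald is used, it carries no information for sparse events

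*SAP*

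**What the plan says.** SAP 6.13.2 sets the scope: "Safety subgroup analysis for common TEAEs and AESI of allergy reaction/hypersensitivity and infections will be summarized by treatment group and overall", in the Period 2 safety population. The model is given as "A logistic regression model with treatment, subgroup, and the interaction of subgroup-by-treatment included as factors will be used", and then: "The subgroup-by-treatment interaction will be tested at the significance level of 0.10. The response variable will be each AE". Fisher's exact test is also run within every subgroup category, whatever the interaction shows. The only limit on inference is subgroup size: a category below 10% of the population is described and not tested. No minimum number of events is given, and no test statistic is named.

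SAP 6.12.2.1 defines a common TEAE as one reaching 1%, "before rounding of total ixekizumab-treated patients". The allergy/hypersensitivity and infection AESIs have no frequency floor.

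The one place where the SAP names a logistic test statistic is 6.1.1, for categorical efficacy and health outcomes: "baseline CRP status in the model using PROC Logistic with a Wald test". That paragraph also falls back on Fisher's exact test when sparse data stop the model from giving a result. SAP 6.13.2 repeats neither rule.

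**The concern.** An interaction test is usually run at 0.10 rather than 0.05 because it is weak and needs some chance to signal. A Wald statistic behaves badly when cells are empty or nearly so: the estimate grows without limit but its standard error grows faster, so the p-value moves towards 1. With events seen in a handful of patients and six cells (three arms by two categories), that is the normal case. The tables would then print large interaction p-values for most rare preferred terms whatever the truth. A reader could take these as evidence that harm does not vary by sex, age, weight or region.

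**Working it through.** **The plan's own figure.** The only power printed is for ASAS40 (Protocol synopsis: 27% versus 7%, 100 per group, two-sided Fisher at 0.05, about 96%). Full binomial enumeration gives 96.5%, so it reproduces. No power is given for the safety interaction test.

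**Inputs from the documents.** About 300 patients randomized 1:1:1 (SAP 5.3), so about 100 placebo and 200 ixekizumab; interaction level 0.10 (6.13.2); common-TEAE floor 1% (6.12.2.1).

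**Assumptions.** Event rates and subgroup shares are not in the documents, so ranges are shown. Subgroups are binary; the BMI, race and four-level region subgroups would be sparser. The three arms are kept separate, giving 2 df.

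**Floor.** 0.01 × 200 = 2 patients. A term with a true 1% rate reaches it with probability 1 − 0.99^200 − 200 × 0.01 × 0.99^199 = 0.595, so rare terms will regularly be tested.

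**How often cells are empty** (no true difference, 50 patients per cell, before applying the floor). At 1%, a cell is empty with probability 0.99^50 = 0.605, so at least one of six is empty with probability 1 − 0.395^6 = 99.6%. At 3%, 0.97^50 = 0.218 and 1 − 0.782^6 = 77%. The damaging case is an empty placebo cell, because both interaction contrasts use it: 1 − 0.395² = 84% at 1%, and 1 − 0.782² = 39% at 3%.

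**Why Wald fails there.** Each contrast is a difference of two log odds ratios, with variance equal to the sum of 1/events + 1/non-events over its four cells. If a placebo cell holds ε events, the estimate grows like log(1/ε) and the variance like 1/ε. The squared ratio behaves like ε(log ε)², which goes to 0.

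Example: 5/30 women in each ixekizumab arm, 0/30 placebo women, and 1/70 men in every arm. The interaction Wald p-value at convergence is above 0.99.

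**Null rejection rate, printed as 10%** (simulated, 100 per arm, subgroup share 20–50%, at least 2 ixekizumab events, 2-df Wald):

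| True incidence | Wald rejection |
|---|---|
| 1–3% | 0.0–0.1% |
| 5% | 0.2–1.0% |
| 10% | 2–6% |

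At the floor itself, enumeration with exactly 2 ixekizumab events and up to 10 placebo events per category gives a smallest three-arm p-value of 0.37, 0.33, 0.27 and 0.103 at subgroup shares of 50%, 30%, 20% and 10%. None reaches 0.10.

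**Power for harm in one subgroup only.** For 1% versus 20%, Wald gives 0.1–0.6%. For a 2% background and 20% in the subgroup it gives 0.7–4.5%.

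**Other statistics.** The ordinary likelihood-ratio test has 32–42% power for 1% versus 20%, but its null rate runs from 4% to 17%, so it can exceed the printed level. Firth penalised likelihood ratio, without an event floor, has a null rate of 1.2–2.4% at 2% incidence, 4.4–6.3% at 5% and 6.6–9.1% at 10%. With a 10-event floor and subgroup shares of 30–50%, its power against harms of this kind was 20–30%, compared with 0.4–4% for Wald.

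**Within-category Fisher** (level 0.05 assumed; category 50%, 30% or 20% of the trial):

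| Harm in the category | Each regimen vs placebo | Pooled ixekizumab vs placebo |
|---|---|---|
| 1% vs 10% | 27%, 6%, 4% | 47%, 19%, 4% |
| 1% vs 20% | 87%, 48%, 32% | 98%, 79%, 49% |

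SAP Table RHBW.6.2 lists each regimen against placebo and an overall comparison for Period 2, not pooled ixekizumab against placebo. In the example, 5/30 versus 0/30 gives p = 0.052; the unlisted pooled contrast, 10/60 versus 0/30, gives p = 0.027.

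**The case against.** **The SAP does not specify Wald for safety.** This stands. SAP 6.13.2 is silent, and the Wald sentence in 6.1.1 covers efficacy and health outcomes. A reader might infer that the rule as written has a level of zero. The documents do not support that: the near-zero figure depends on Wald, and a likelihood-ratio test behaves quite differently. The silence is itself part of the point, because the choice changes the result materially.

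**The sparse-data fallback in 6.1.1.** If Wald is borrowed from that paragraph, its fallback should be considered too. It does not rescue the test. A fit with an empty cell can still print a p-value near 1, and Fisher's exact test as described does not test an interaction.

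**One empty cell need not disable the test.** Correct. With 50 per cell, take placebo events of 4 and 1, one regimen 1 and 0, and the other 1 and 9. The surviving contrast is (−1.516 + 3.892) − (−3.892 + 2.442) ≈ 3.83 with variance 2.45. This gives a Wald statistic of 5.98 and a 2-df p of 0.050, which rejects. The share of datasets with an empty cell is therefore not the share in which the test is dead; the simulated rates are the relevant measure.

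**The section is not blind to harm.** A reader might infer that no subgroup-specific harm could be flagged. That is too strong. With incidence around 10% or more the test works, though weakly: across the three-arm and pooled versions, power is 21–52% for 10% versus 30%. The Fisher tests run regardless and can show a large harm, but they are weaker per regimen and do not test whether categories differ.

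**No decision depends on it.** The analysis is exploratory, and nowhere does the SAP say that non-significance will be read as consistency. That limits the weight of the point.

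**Conclusion.** The point holds for sparse events and conditionally on Wald. For terms at about 5% incidence or less, the nominal 10% test rejects about 0–1% of the time under no interaction, and has under 1% power for a 1% versus 20% harm in one category. Its p-value then says nothing about consistency. At about 10% incidence it is conservative but usable.

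The result rests on assumed event rates, binary subgroups at 20–50% of patients, and three separate arms. Pooling the regimens raises Wald power for 1% versus 20% to at most about 5%. The claim that the section as a whole cannot detect a subgroup-specific harm is not supported, and the primary analysis is unaffected.

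The efficacy interaction test in SAP 6.13.1 ("The treatment-by-subgroup interaction will be tested at the 10% significance level") shows a milder version: for ASAS40 at 7/27/27%, Wald rejects 5.6–6.9% at shares of 20–50%. Changing it is optional.

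**What to change.** In SAP 6.13.2, state that the interaction is tested by a Firth penalised likelihood-ratio test, comparing penalised likelihoods with and without the interaction terms. Restrict it to events reaching a prespecified minimum count, for example 10 patients across the three arms. The value 10 is a judgement, and what matters is fixing it in advance. Apply the same floor to the allergy and infection AESIs. Below the floor, show counts and risk differences with confidence intervals by subgroup and print no interaction p-value. Add that a non-significant interaction is not to be read as consistency of effect.

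The same test could be used for ASAS40 and ASAS20 in 6.13.1 as a refinement.

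The cost is a few sentences and a procedure option, with no new data. Rare TEAEs would carry no interaction p-value, a few more interactions may go to medical review, and Firth remains somewhat conservative when events are sparse.

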6.14. Protocol Deviations

Protocol deviations will be identified throughout the study. Important protocol deviations are defined as those violations from the protocol likely to have a significant impact on the completeness, accuracy, and/or reliability of the study data or that may significantly affect a subject's rights, safety, or well-being.

Table RHBW.6.12 includes the categories and subcategories of important protocol deviations, whether or not these deviations will result in the exclusion of patients from PPS and the source of identification for the deviations for the CSR.

The number and percentage of patients having important protocol deviation(s) will be summarized within category and subcategory of deviations by treatment group for:

- Period 2 (ITT Population)
- Period 3 (Extended Treatment Period Population)

A by-patient listing of important protocol deviations will be provided.

Table RHBW.6.12. Identification and Action of Important Protocol Deviations

Important Protocol Deviation Category/Subcategory/Study Specific	Action for PPS Analysis	Source to Identify Protocol Deviation ^a
Category: Eligibility		
Sub-Category: Inclusion/Exclusion		
[1] No established diagnosis of rad-axSpA at screening	Exclude from PPS	Monitor and Stats
[2] History of back pain <3 months or age at onset ≥ 45 years	Exclude from PPS	Monitor and Stats
[3] No active rad-axSpA defined as BASDAI ≥ 4 and total back pain ≥ 4 on an NRS at screening and baseline	Exclude from PPS	Monitor and Stats
[4] No prior TNF inhibitor OR more than 2 TNF inhibitors OR the patients have not discontinued at least 1 TNF inhibitor due to either intolerance or an inadequate response	Exclude from PPS	Monitor and Stats
[5] Not have had an inadequate response to 2 or more NSAIDs at therapeutic dose range for a total duration of at least 4 weeks AND not have history of intolerance to NSAID	Exclude from PPS	Monitor
[6] Not have a history of prior therapy for axSpA of at least 12 weeks before screening	Exclude from PPS	Monitor and Stats
[7] Not have stable dose for NSAID or COX-2 for at least 2 weeks before baseline randomization, if taking NSAID or Cox-2 inhibitors	Only Exclude from PPS if 1. Stopped or decreased dose for a current one <3 days before randomization; 2. Start or increased dose for a current one or started a new one <2 weeks before randomization.	Monitor and Stats
[8] Not ≥ 18 years of age at time of screening	Exclude from PPS	Monitor and Stats
[9] Female patient of childbearing potential with positive pregnancy test; or did not use a reliable method of birth control, if applicable	Do not exclude from PPS	Monitor and Stats
[11] Have total ankylosis of the spine at screening	Exclude from PPS	Monitor
[12] Have a history of other systemic inflammatory diseases or other chronic pain conditions that might confound the evaluations of benefit from ixekizumab therapy	Exclude from PPS	Monitor

Important Protocol Deviation Category/Subcategory/Study Specific	Action for PPS Analysis	Source to Identify Protocol Deviation^a
[13] Have active Crohn’s disease (CD) or active ulcerative colitis (UC) at screening	Do not exclude from PPS	Monitor and Stats
[14] Have evidence of active anterior uveitis (an acute episode) within the last 4 weeks before baseline randomization	Do not exclude from PPS	Monitor and Stats
[15] Have current or a history of lymphoproliferative disease, or signs or symptoms of lymphoproliferative disease; or have active or history of malignant disease within 5 years before V2	Do not exclude from PPS	Monitor
[16] Have had fluid overload, MI or new onset ischemic heart disease, uncompensated heart failure, or other serious cardiac disease within 12 weeks before V2	Do not exclude from PPS	Monitor
[17] Presence of significant, uncontrolled cerebro-cardiovascular events at screening	Do not exclude from PPS	Monitor
[18] Presence of respiratory, hepatic, renal, gastrointestinal, endocrine, hematologic disorder at screening that pose unacceptable risk to patient or interfering with interpretation of data	Do not exclude from PPS	Monitor
[19] Presence of neurologic or neuropsychiatric disorders at screening that pose unacceptable risk to patient or interfering with interpretation of data	Do not exclude from PPS	Monitor
[20] Presence of significant uncontrolled neuropsychiatric disorder, recent history (30 days before V1 and anytime between V1 and V2) of a suicide attempt, have a score of 3 on Item 12 (Thoughts of Death or Suicide) of the QIDS-SR16 at V1 or V2, or at risk for suicide	Do not exclude from PPS	Monitor and Stats
[21] Deleted in protocol.		
[22] In the past 12 weeks before V2, had a serious infection, hospitalization or IV antibiotics for an infection; in the past 24 weeks before V2, had a serious bone or joint infection, ever had an infection of an artificial joint, or infection that occurs with increased incidence in an immunocompromised host	Do not exclude from PPS	Monitor
[23] Have a known immunodeficiency or are immunocompromised to an extent such that participation in the study would pose an unacceptable risk to the patient	Do not exclude from PPS	Monitor
[24] Have or had a herpes zoster or any other clinically apparent varicella-zoster virus infection within 12 weeks of V2	Do not exclude from PPS	Monitor
[25] Have any other active or recent infection within 4 weeks of V2 that would pose an unacceptable risk to the patient	Do not exclude from PPS	Monitor
[26] Have a known allergy or hypersensitivity to any biologic therapy that would pose an unacceptable risk to the patient if participating in this study	Exclude from PPS	Monitor
[27] Have had surgical treatment of a joint to be assessed in the study within 8 weeks before	Exclude from PPS depending on the clinical	Monitor

Important Protocol Deviation Category/Subcategory/Study Specific	Action for PPS Analysis	Source to Identify Protocol Deviation^a
baseline randomization or will require such during the first 16 weeks of the trial	significance	
[28] Had any major surgery within 8 weeks before V2, or will require such during the study that would pose an unacceptable risk to the patient	Do not exclude from PPS	Monitor
[29] Have received cDMARDs, and/or other therapies such as but not limited to: gold salts, cyclosporine, azathioprine, dapsone, 6-mercaptopurine, mycophenolate mofetil, or any other immunosuppressive agents within 4 weeks before baseline randomization.	Exclude from PPS 
 1. Stopped or decreased dose for a current one ≤ 3 days before randomization; or 2. Start new treatment or increased dose for current one or started a new one < 4 weeks before randomization. 	Monitor and Stats
[30] Current use of oral corticosteroids > 10 mg/day prednisone or its equivalent	Exclude from PPS 
 1. If dose > 10mg/day any time within 4 weeks; or 2. Stopped or decreased dose for a current one < 10 days before randomization; or 3. Start new treatment or increased dose for current one or started a new one < 4 weeks before randomization; 	Monitor and Stats
[31] Have received any prior, or are currently receiving, treatment with biologic or other immunomodulatory agents, including investigational therapies (such as but not limited to Janus kinase (JAK) inhibitors, IL-1, IL-6, IL-23, IL-17 (including ixekizumab), IL-17R, T cell, or B cell targeted therapies)	Exclude from PPS	Monitor and Stats
[32] Are currently enrolled in, have participated, or discontinued from a clinical trial involving an investigational product (IP) or nonapproved use of a drug or device within the last 30 days before screening or a period of at least 5 half-lives of the last administration of the drug, whichever is longer; for Brazil patients, patients completed a clinical trial involving an IP or nonapproved use of drug or device unless there is direct benefit to patient	Exclude from PPS	Monitor
[33] Are currently (for all sites except Brazil sites) or concurrently (for Brazil sites, unless	Exclude from PPS	Monitor

Important Protocol Deviation Category/Subcategory/Study Specific	Action for PPS Analysis	Source to Identify Protocol Deviation^a
there is direct benefit to patient) enrolled in any other clinical trial involving an investigational product or any other type of medical research judged not to be scientifically or medically compatible with this study		
[34] Are currently receiving or have received treatment with denosumab within 6 months before baseline randomization	Do not exclude from PPS	Monitor and Stats
[35] Have received any parenteral glucocorticoid administered by intra-articular, intramuscular, or IV injection within 6 weeks before baseline randomization, or a parenteral injection of glucocorticosteroids is anticipated during the Period 2	Exclude from PPS	Monitor and Stats
[36] Use of any opiate analgesic at average daily doses >30 mg/day of morphine or its equivalent or use of variable doses of any opiate analgesic within 6 weeks before baseline randomization.	Exclude from PPS 1. If doses >30 mg/day any time within 6 weeks before randomization; or 2. Stopped or decreased dose for a current one <7 days before randomization; 3. Start new treatment or increased dose for current one or started a new one <6 weeks before randomization.	Monitor and Stats
[37] Had a live vaccination or participated in a vaccine clinical study within 12 weeks before V2, or intend to have a live vaccination during the study or within 12 weeks of completing study treatment	Do not exclude from PPS	Monitor
[38] Had a vaccination with BCG within 12 months before V2, or intend to have this vaccination with BCG during the study or within 12 months of completing study treatment	Do not exclude from PPS	Monitor and Stats
[39] Have a body temperature $\geq 38^{\circ}\text{C}$ (100.5°F) at V2	Do not exclude from PPS	Monitor and Stats
[40] Have evidence or suspicion of active or latent TB	Do not exclude from PPS	Monitor
[41] Are positive for human immunodeficiency virus serology (HIV)	Do not exclude from PPS	Monitor and Stats
[42] Have evidence of or test positive for hepatitis B virus (HBV) and are HBV DNA	Do not exclude from PPS	Monitor and

Important Protocol Deviation Category/Subcategory/Study Specific	Action for PPS Analysis	Source to Identify Protocol Deviation^a
positive		Stats
[43] Have evidence of or test positive for hepatitis C virus (HCV)	Do not exclude from PPS	Monitor and Stats
[44] Have ECG abnormalities that are considered clinically significant and would pose an unacceptable risk to the patient if participating in the study	Do not exclude from PPS	Monitor
[45] At V1, have a neutrophil count <1.50 GI/L	Do not exclude from PPS	Monitor and Stats
[46] At V1, have a lymphocyte count <0.80 GI/L;	Do not exclude from PPS	Monitor and Stats
[47] At V1, have a platelet count <100 GI/L	Do not exclude from PPS	Monitor and Stats
[48] At V1, have aspartate aminotransferase (AST) or alanine aminotransferase (ALT) >2.5 times the upper limit of normal (ULN)	Do not exclude from PPS	Monitor and Stats
[49] At V1, have a total white blood cell (WBC) count <3.00 GI/L	Do not exclude from PPS	Monitor and Stats
[50] At V1, have hemoglobin <8.5 g/dL for male patients and <8.0 g/dL for female patients	Do not exclude from PPS	Monitor and Stats
[51] Have other clinical laboratory test results at V1 that are outside the normal reference range for the population and are considered clinically significant	Do not exclude from PPS	Monitor
[52] Have donated >450 mL of blood within the last 4 weeks before V1, or intend to donate blood during the course of the study	Do not exclude from PPS	Monitor
[53] Are women who are lactating or breastfeeding	Do not exclude from PPS	Monitor
[54] Are investigator-site personnel directly affiliated with this study and/or their immediate families	Exclude from PPS	Monitor
[55] Are Lilly employees or its designee or are employees of third-party organizations (TPOs) involved in the study	Exclude from PPS	Monitor
[56] Are unwilling or unable to comply with the use of a data collection device to directly record data from the patient,	Exclude from PPS when occurred in Period 2	Monitor
[57] Have any other condition that precludes the patient from following and completing the protocol	Exclude from PPS	Monitor
[58] Patients having contraindications to MRI (This is only for MRI addendum countries)	Do not exclude from PPS	Monitor

Important Protocol Deviation Category/Subcategory/Study Specific	Action for PPS Analysis	Source to Identify Protocol Deviation^a
Sub-Category: Other		
Rescreened patients were enrolled but did not meet rescreening criteria per protocol.	Do not exclude from PPS	Monitor
Category: Study Procedures		
Sub-Category: Violation of Discontinuation Criteria		
[D1] Lilly medical not consulted when patient met hepatic lab criteria for consideration of discontinuation	Do not exclude from PPS	Monitor
[D2-N] Neutrophil counts <0.50 GI/L, or ≥0.50 GI/L and <1.00 GI/L based on 2 test results within 1 week of knowing 1 st result, or ≥1.00 GI/L and <1.50 GI/L based on 3 test results and a concurrent infection	Do not exclude from PPS	Monitor and Stats
[D2-W] Total WBC count <2.00 GI/L	Do not exclude from PPS	Monitor and Stats
[D2-L] Lymphocyte count <0.50 GI/L	Do not exclude from PPS	Monitor and Stats
[D2-P] Platelet count <50 GI/L	Do not exclude from PPS	Monitor and Stats
[D3] Patient experiences a severe AE, an SAE, or a clinically significant change in a laboratory value that merits the discontinuation of the investigational product and appropriate measures being taken	Do not exclude from PPS	Monitor
[D4] Clinically significant systemic hypersensitivity reaction does not respond to treatment	Do not exclude from PPS	Monitor
[D5] Patient became pregnant	Do not exclude from PPS	Monitor
[D6] Patient developed a malignancy (Patients may be allowed to continue if they develop no more than 2 nonmelanoma skin cancers during the study)	Do not exclude from PPS	Monitor
[D7] Enrolled in prohibited medical research	Exclude from PPS when occurred in Period 2	Monitor
[D11] Lilly stopped the patient participation	Do not exclude from PPS	Monitor
[D12] Patient became HBV DNA positive	Do not exclude from PPS	Monitor
[D13] Patient developed a clinically significant infection during study participation for patients from UK sites	Do not exclude from PPS	Monitor
[D14] Patient received a live vaccination during the course of the study for patients from UK	Do not exclude from PPS	Monitor

Important Protocol Deviation Category/Subcategory/Study Specific	Action for PPS Analysis	Source to Identify Protocol Deviation^a
sites		
Category: Study Procedures		
Sub-Category: Excluded Con-meds	Exclude from PPS (Excluded Con-meds refers to clinically meaningful change in con-meds [Appendix 13] when occurred during Period 2 and prescribed for primary study condition) Excluded Con-meds in Period 3 refer to the lists in Appendix 13 .	Monitor and Stats
Sub-Category: Lab/Imaging Criteria		
Missing imaging as per protocol schedule of events	Do not exclude from PPS	Monitor
Missing lab chemistry and hematology: missing baseline or not having at least 1 postbaseline	Do not exclude from PPS	Stats
Sub-Category: Other		
Missing QIDS total score: missing baseline or any scheduled visit before discontinuation visit	Do not exclude from PPS	Stats
Missing Columbia scale at any visit except V1	Do not exclude from PPS	Monitor and Stats
Missing ASAS components for ASAS40 derivation: not having Week 16 measurement for patients who have completed Week 16	Do not exclude from PPS. Note: if missing ASAS components lead to missing ASAS40, such patient will be treated as nonresponder for the Week 16 ITT analyses	Stats
Had unqualified site personnel perform clinical safety and/or efficacy assessments	Do not exclude from PPS	Monitor
Category: Investigational Product		
Sub-Category: Treatment Assignment/Randomization Error		
Took incorrect study medication	Do not exclude from PPS. Analyze ‘As randomized’ or ‘As assigned’.	Monitor and Stats
Sub-Category: Compliance	Exclude from PPS when occurred during Period 2	Stats

Important Protocol Deviation Category/Subcategory/Study Specific	Action for PPS Analysis	Source to Identify Protocol Deviation ^a
Sub-Category: Patient took medication not fit for use	Do not exclude from PPS	Monitor
Sub-Category: Unblinding	Exclude from PPS	Monitor
Sub-Category: Other		
Randomized but did not take any study medication	Exclude from PPS	Stats
Category: Safety		
Sub-Category: SAEs	Do not exclude from PPS	Monitor
Category: Informed Consent		
Sub-Category: Informed Consent not Obtained/Missing/Late	Exclude from PPS	Monitor and Stats
Subcategory: Improper Informed Consent	Do not exclude from PPS	Monitor
Category: Administrative/Oversight		
Sub-Category: Reg/Ethic Approvals	Exclude from PPS	Monitor
Sub-Category: Other		
Enrolled in a site with significant GCP non-compliance issue	Exclude from PPS	Monitor

Abbreviations: AE = adverse event; axSpA = axial spondyloarthritis; ASAS = Assessment of Spondyloarthritis International Society; BASDAI = Bath Ankylosing Spondylitis Disease Activity Index; BCG = Bacille de Calmette et Guérin; BSA = body surface area; cDMARD = conventional disease-modifying antirheumatic drug; ECG = electrocardiogram; eCRF = electronic case report form; GCP = good clinical practice; IL = interleukin; ITT = intent-to-treat; IV = intravenous; IWRS = interactive web-response system; NSAID = nonsteroidal anti-inflammatory drug; MI = myocardial infarction; NRS = numerical rating scale; PCP = pneumocystis pneumonia; PPS = per protocol set; QIDS-SR16 = Quick Inventory of Depressive Symptomatology–Self-Report 16 items; rad = radiographic; TB = tuberculosis; V = visit; WBC = white blood cell.

^a The term “Monitor” indicates the protocol deviation will be identified by site monitors and entered into monitor’s list using a spreadsheet. The spreadsheet will be exported as Study Data Tabulation Model (SDTM) DV domain.

The term “Stats” indicates the protocol deviation will be programmed based on data in clinical database by statistical programmers with the statistical programming guidance provided. The detailed programming specification will be documented in Analysis Data Model (ADaM) specification.

[figure not shown]
The terms “Monitor and Stats” indicates the protocol deviation will be a combination of monitor’s list (SDTM.DV domain) and statistical programming from clinical database, the deviation will show if either source identifies.

